### **Treatment of Outliers during Pharmacokinetic Analysis**

Application of this procedure to all pharmacokinetic analyses is not a requirement. Rather, this procedure provides justification for exclusion of data when scientifically appropriate. This procedure describes the methodology for identifying an individual value as an outlier for potential exclusion, but does not require that the value be excluded from analysis. The following methodology will not be used to exclude complete profiles from analysis.

#### Data within an Individual Profile

A value within an individual profile may be excluded from analysis if any of the following criteria are met:

- For pharmacokinetic profiles during multiple dosing, the concentration of the pre-dose sample exceeds all measured concentrations for that individual in the subsequent post-dose samples.
- For pharmacokinetic profiles during single dosing of non-endogenous compounds, the concentration in a pre-dose sample is quantifiable.
- For any questionable datum that does not satisfy the above criteria, the profile will be evaluated and results reported with and without the suspected datum.

#### Data between Individual Profiles

1. If  $n < 6$ , then the dataset is too small to conduct a reliable range test. Data will be analyzed with and without the atypical value, and both sets of results will be reported.
2. If  $n \geq 6$ , then an objective outlier test will be used to compare the atypical value to other values included in that calculation:
  - a. Transform all values in the calculation to the logarithmic domain.
  - b. Find the most extreme value from the arithmetic mean of the log transformed values and exclude that value from the dataset.
  - c. Calculate the lower and upper bounds of the range defined by the arithmetic mean  $\pm 3 \times \text{SD}$  of the remaining log-transformed values.
  - d. If the extreme value is within the range of arithmetic mean  $\pm 3 \times \text{SD}$ , then it is not an outlier and will be retained in the dataset.
  - e. If the extreme value is outside the range of arithmetic mean  $\pm 3 \times \text{SD}$ , then it is an outlier and will be excluded from analysis.

If the remaining dataset contains another atypical datum suspected to be an outlier and  $n \geq 6$  following the exclusion, then repeat step 2 above. This evaluation may be repeated as many times as necessary, excluding only one suspected outlier in each iteration, until all data remaining in the dataset fall within the range of arithmetic mean  $\pm 3 \times \text{SD}$  of the log-transformed values.

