### **9.3 Pharmacokinetic Assessment**

#### **9.3.1 Pharmacokinetic Analysis**

Pharmacokinetic parameter estimates will be determined using non-compartmental procedures in validated software program (Phoenix WinNonlin Version 6.4 or later).

Plasma concentrations of lasmiditan (LY573144) and its metabolites will be used to determine the following PK parameters, when possible:

Parameter	Units	Definition
$C_{\max}$	ng/mL	maximum observed drug concentration
$t_{\max}$	h	time of maximum observed drug concentration
$AUC(0-\infty)$	ng.h/mL	area under the concentration versus time curve from time zero to infinity
$AUC(0-t_{\text{last}})$	ng.h/mL	area under the concentration versus time curve from time zero to time $t$ , where $t$ is the last time point with a measurable concentration
% $AUC(t_{\text{last}}-\infty)$	%	percentage of $AUC(0-\infty)$ extrapolated
$t_{\frac{1}{2}}$	h	half-life associated with the terminal rate constant ( $\lambda_z$ ) in non-compartmental analysis
CL/F	L/h	apparent total body clearance of drug calculated after extra-vascular administration (LY573144 only)
$V_z/F$	L	apparent volume of distribution during the terminal phase after extra-vascular administration (LY573144 only)
$V_{ss}/F$	L	apparent volume of distribution at steady state after extra-vascular administration (LY573144 only)
MR		Metabolic ratio a

a no molar correction will be applied since the metabolites are very similar in molecular weight and within 5% of the molecular weight for lasmiditan.

Plasma concentrations of propranolol will be used to determine the following PK parameters, when possible:

Parameter	Units	Definition
$C_{\max}$	ng/mL	maximum observed drug concentration
$t_{\max}$	h	time of maximum observed drug concentration
$AUC_{\tau}$	ng.h/mL	area under the concentration versus time curve during one dosing interval
CL/F	L/h	apparent total body clearance of drug calculated after extra-vascular administration

Additional PK parameters may be calculated, as appropriate. The software and version used for the final analyses will be specified in the clinical study report. Any exceptions or special handling of data will be clearly documented within the final study report.

Formatting of tables, figures and abbreviations will follow the Eli Lilly Global PK/PD/TS Tool: NON-COMPARTMENTAL PHARMACOKINETIC STYLE GUIDE. The version of the tool effective at the time of PK analysis will be followed.

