#### Reporting of Excluded Values

Individual values excluded as outliers will be documented in the final report. Approval of the final report will connote approval of the exclusion.

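### The PK outlier rule both mandates and disclaims exclusion, and at n ≥ 6 it does not require the result with the value retained

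*SAP*

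**What the plan says.** The outlier procedure is in SAP Section 9.3.1. Its opening paragraph (Treatment of Outliers during Pharmacokinetic Analysis) makes use of the procedure optional. It adds that finding an outlier "does not require that the value be excluded from analysis", and sets one limit: "The following methodology will not be used to exclude complete profiles from analysis".

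Under Data between Individual Profiles there are two branches:

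- **n < 6:** no test is run. "Data will be analyzed with and without the atypical value, and both sets of results will be reported".
- **n ≥ 6:** a test is used to "compare the atypical value to other values included in that calculation". The most extreme log value is left out, and mean ± 3 SD is computed from the rest. If the value lies outside that range, "then it is an outlier and will be excluded from analysis". The test may be repeated, one value at a time, while n stays at 6 or more.

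Under Data within an Individual Profile, for a doubtful value that meets neither listed criterion, "the profile will be evaluated and results reported with and without the suspected datum".

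On reporting, "Individual values excluded as outliers will be documented in the final report" (Reporting of Excluded Values), and more generally "Any exceptions or special handling of data will be clearly documented within the final study report" (Section 9.3.1). Section 9.1 provides for listing all databased data, and Section 13.1 for reporting individual derived PK parameters. Section 9.3.2 answers the PK objectives with geometric mean ratios and 90% CIs, and allows further analyses without requiring any.

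**The concern.** There are two linked problems.

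First, step 2e reads as an instruction and the opening paragraph reads as a permission. Two analysts with the same flagged value could treat it differently, and each could cite the SAP. The 3 SD limit is objective, but it is not clear whether crossing it decides the exclusion or only allows it.

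Second, the duty to show both results is attached to the small-sample branch and to some within-profile data, but not to the branch this study will use. In an interaction study, the values most likely to be flagged include those of subjects with an unusually large true change on coadministration. Removing them pulls the ratio and its upper confidence limit down. A reader would learn that values were removed, but the report need not give the estimate that includes them.

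**Working it through.** **1. Which branch applies.** SAP Section 7 plans 36 completers and up to 44 enrolled, so n ≥ 6.

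**2. What each part of the procedure requires.**

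| Situation | Exclusion | Result with value retained |
|---|---|---|
| Opening paragraph | not required | not addressed |
| Within profile, doubtful value meeting neither criterion | not stated | required |
| Between profiles, n < 6 | no test | required |
| Between profiles, n ≥ 6 (step 2e) | mandatory as worded | not required; documentation only |

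The opening paragraph makes two separate statements: using the procedure is optional, and a value it identifies need not be excluded. Step 2e is compatible with the first but not with the second.

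**3. How often the test removes a value from clean data.** The SAP gives no figure. For normal log data, the chance that a given value falls outside the limits set by the others is p = 2 × P(T with n − 2 df > 3/√(1 + 1/(n − 1))).

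- n = 36: 3/√(1 + 1/35) = 2.958, p = 0.0056, and n × p = 0.202.
- n = 44: 3/√(1 + 1/43) = 2.966, p = 0.0050, and n × p = 0.218.

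Simulating the full iterative rule (20,000 datasets per n) gives 0.20 at n = 36 and 0.21 at n = 44. This assumes that every dataset is tested. The SAP tests only an atypical value, so about 20% is an upper bound. If only values beyond 1.5, 2 or 3 IQR from the quartiles are tested, it falls to 18%, 9% or 0.8% at n = 36.

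**4. Effect on the ratio if a few subjects truly respond.** The inputs below are assumptions, because the SAP gives no PK variability: log SD between/within subjects of 0.30/0.20, 0.40/0.20 or 0.50/0.25; n = 36; 2 subjects with a true Day 9 rise; no effect in the other 34; each day's values tested in every dataset.

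With all data kept, the expected ratio is fold^(2/36): 4^(1/18) = 1.080, 3^(1/18) = 1.063, 2^(1/18) = 1.039.

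Simulation of the Section 9.3.2 model (2,000 replicates per setting), 4-fold rise:

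| Between/within SD | All data (90% CI) | After rule (90% CI) | Responder values removed |
|---|---|---|---|
| 0.30/0.20 | 1.082 (0.959–1.220) | 1.017 (0.930–1.113) | 76% |
| 0.40/0.20 | 1.080 (0.958–1.218) | 1.038 (0.938–1.149) | 48% |
| 0.50/0.25 | 1.081 (0.945–1.235) | 1.055 (0.932–1.195) | 27% |

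As a rough check, if a fraction f of responder values is removed, the ratio should be near 4^((1 − f)/18). This gives 1.019, 1.041 and 1.058, close to the simulated values.

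Smaller effects:

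- 3-fold rise: 1.061 to 1.028, 1.062 to 1.043, 1.061 to 1.050.
- 2-fold rise: 1.038 to 1.031, 1.040 to 1.036, 1.037 to 1.035, so every change is below 0.01.
- 4-fold rise, testing only values beyond 3 IQR: 1.079 to 1.058 at 0.30/0.20, and 1.081 to 1.077 at 0.50/0.25.
- No responders (0.30/0.20): mean ratio unchanged, and 90% CI coverage 0.900 after the rule.

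**The case against.** The best defence is that the opening paragraph governs: the procedure is optional, it exists to justify exclusions, and step 2e only describes what follows once it is invoked. That makes the conflict mild but does not remove it, because the opening paragraph also disclaims the exclusion itself.

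The defence is stronger on consequences, and these parts stand. Exclusions must be documented. Databased data are listed and individual PK parameters reported, so a reader could in principle identify the value and recompute the estimate. Further analyses are allowed. A subject with a true 4-fold rise would probably have the whole Day 9 profile raised, and removing that subject's Cmax and AUC together comes close to excluding a complete profile, which the SAP forbids. If the bar covers such values, the effect is nil. In every 4-fold setting above, the 90% CI includes 1 both before and after the rule.

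A reader might infer four stronger claims that the SAP does not support:

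- **That the test applies to within-subject differences.** This would take the ratio almost to 1.00, but the procedure compares values between individual profiles, and a difference is not a value from one profile.
- **That the rule on AUC(0-∞) values left out of summaries (General PK Parameter Rules) shows single AUCs may be dropped as outliers.** That sentence follows the flag for more than 20% extrapolation and does not refer to this test.
- **That one dataset in five will lose a genuine value.** That holds only if every dataset is tested.
- **That exclusions could be hidden.** The documentation duty rules this out.

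**Conclusion.** The wording conflict and the reporting gap are both present in the text and do not depend on any assumption. Their practical weight is low. They affect only the secondary and exploratory PK results, for which the SAP sets no decision limit. The primary heart-rate analysis is outside this procedure. An interaction shared by all subjects would not be removed.

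The numerical effect is conditional. A move from about 1.08 to between 1.02 and 1.06 needs the assumed log SDs, two 4-fold responders among 36, and testing of every dataset by day. With a 2-fold rise, a strict trigger, or the protective reading of the bar on complete profiles, it is small or nil. The point is worth correcting because the SAP already applies the missing safeguard in its other branches.

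**What to change.** Make two changes under Data between Individual Profiles:

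1. Align step 2e with the opening paragraph, for example: *a value outside mean ± 3 SD is flagged as a potential outlier and may be excluded if a scientific reason is documented.* In the repeat step, a flagged value is then set aside for the next round of the test only.
2. Add: *Whenever a value is excluded at n ≥ 6, the geometric mean ratios and 90% CIs will be reported with and without it.*

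The second sentence carries most of the protection, because it works whichever way step 2e is reconciled. While the text is open, it would help to say which set of values is tested and whether the bar on complete profiles covers a subject's Cmax and AUC.

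The cost is a short wording change and one conditional sensitivity table, produced only if a value is excluded. No new data are needed.

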#### Reporting of Excluded Values

Individual values excluded as outliers will be documented in the final report. Approval of the final report will connote approval of the exclusion.

#### **9.3.2 Pharmacokinetic Statistical Methodology**

Pharmacokinetic parameters will be evaluated to determine the impact of propranolol coadministration on the PK of a single dose of lasmiditan and its metabolites. Log-transformed  $C_{\max}$ ,  $AUC(0-\infty)$ , and  $AUC(0-t_{last})$  parameters will be evaluated in a linear mixed-effects model with a fixed effect for treatment (lasmiditan coadministered with propranolol [Day 9; test treatment] versus lasmiditan alone [Day 1; reference treatment]), and a random effect for subject. The treatment differences will be back-transformed to present the ratios of geometric means and the corresponding 90% CI.

An example of the SAS code that will be used is as follows:

```
proc mixed data=xxx;
  class trtmnt subject;
  model l_pk = trtmnt / alpha=0.1;
  random subject;
  lsmeans trtmnt / pdiff;
run;
```

where l\_pk is the log-transformed (base e) PK parameter.

The  $t_{max}$  will be analyzed using a Wilcoxon signed rank test. Estimates of the median difference based on the observed medians, 90% CIs and p-values from the Wilcoxon test will be calculated.

A similar analysis will be performed to determine the impact of coadministration of a single dose of lasmiditan on the steady-state PK of propranolol. The model will include the following treatments: propranolol coadministered with lasmiditan (Day 9; test treatment) versus propranolol alone (Day 8; reference treatment).

Additional analyses may be performed, as warranted.

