## 7. SAMPLE SIZE JUSTIFICATION

Up to 44 subjects may be enrolled to ensure 36 subjects complete the study. Assuming a standard deviation for the change in HR of 10.9 (based on previous studies [H8H-MC-CD-LAHO and H8H-CD-LAHJ]), this will result in a 90% probability that the half-width of the 90% confidence interval (CI) about the mean within-subject change is no larger than 5 beats per minute (bpm). Subjects who are randomized but do not complete the study may be replaced to ensure that enough subjects complete the study.

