## General PK Parameter Rules

- Actual sampling times will be used in the final analyses of individual PK parameters, except for non-bolus predose sampling times which will be set to zero. For non-bolus, multiple dose profiles, the predose time will be set to zero unless a time deviation falls outside of the protocol blood collection time window which is considered to impact PK parameter derivation.
- $C_{\max}$  and  $t_{\max}$  will be reported from observed values. If  $C_{\max}$  occurs at more than one time point,  $t_{\max}$  will be assigned to the first occurrence of  $C_{\max}$ .
- AUC parameters will be calculated using a combination of the linear and logarithmic trapezoidal methods (linear-log trapezoidal rule). The linear trapezoidal method will be applied up to  $t_{\max}$  and then the logarithmic trapezoidal method will be used after  $t_{\max}$ . The minimum requirement for the calculation of AUC will be the inclusion of at least three consecutive plasma concentrations above the lower limit of quantification (LLOQ), with at least one of these concentrations following  $C_{\max}$ . AUC(0-∞) values where the percentage of the total area extrapolated is more than 20% will be flagged. Any AUC(0-∞) value excluded from summary statistics will be noted in the footnote of the summary table.
- Half-life ( $t_{1/2}$ ) will be calculated, when appropriate, based on the apparent terminal log-linear portion of the concentration-time curve. The start of the terminal elimination phase for each subject will be defined by visual inspection and generally will be the first point at which there is no systematic deviation from the log-linear decline in plasma concentrations. Half-life will only be calculated when a reliable estimate for this parameter can be obtained comprising of at least 3 data points. If  $t_{1/2}$  is estimated over a time window of less than 2 half-lives, the values will be flagged in the data listings. Any  $t_{1/2}$  value excluded from summary statistics will be documented in the footnote of the summary table.
- A uniform weighting scheme will be used in the regression analysis of the terminal log-linear portion of the concentration-time curve.
- The parameters based on predicted  $C_{\text{last}}$  will be reported.

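### The planned tmax estimate, taken from observed medians, is not tied to the signed-rank interval and p-value beside it, and its wording allows two different estimators

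*SAP*

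**What the plan says.** SAP section 9.3.2 (Pharmacokinetic Statistical Methodology) says that tmax "will be analyzed using a Wilcoxon signed rank test" and continues: "Estimates of the median difference based on the observed medians, 90% CIs and p-values from the Wilcoxon test will be calculated". The comparisons are within subject. For lasmiditan and its metabolites the contrast is "lasmiditan coadministered with propranolol [Day 9; test treatment] versus lasmiditan alone [Day 1; reference treatment"; for propranolol, under what the section calls a similar analysis, it is "propranolol coadministered with lasmiditan (Day 9; test treatment) versus propranolol alone (Day 8; reference treatment".

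The General PK Parameter Rules in section 9.3.1 say that Cmax and tmax "will be reported from observed values", and that actual sampling times are used. On numbers, section 7 states: "Up to 44 subjects may be enrolled to ensure 36 subjects complete the study".

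The SAP does not define the estimator further, say how the interval is constructed, or say how zero differences are treated. The example SAS code in section 9.3.2 covers only the mixed model for the log-transformed parameters.

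**The concern.** A confidence interval from the signed-rank test is found by inverting that test on the paired differences. It covers their pseudo-median, and the estimate that belongs to it is the median of the Walsh averages (Hodges-Lehmann). Section 9.3.2 takes the interval and p-value from the test but the estimate from somewhere else.

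If the estimate is the difference between the two treatment medians, it discards the pairing that the interval uses, and nothing keeps it inside the limits. A results row could then show no change in tmax next to an interval that excludes zero. If tmax is analysed for every analyte, there are five such rows: lasmiditan, M7, M8, M18 and propranolol.

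The sentence can also be taken to mean the median of the within-subject differences. Two programmers could therefore follow the plan and report different numbers.

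**Working it through.** The SAP gives no figure for tmax, so there is nothing to reproduce. The check has three steps.

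**1. The interval for 36 pairs.** The number of pairs is the completer target in section 7. With differences d1 to d36 there are 36 × 37 / 2 = 666 Walsh averages (di + dj)/2. The Hodges-Lehmann estimate is their median. The 90% limits are the k-th smallest and k-th largest. The normal approximation is k ≈ 666/2 − 1.645 × √(36 × 37 × 73 / 24) = 333 − 1.645 × 63.65 = 228.3; the exact distribution gives k = 228. The Hodges-Lehmann estimate lies between these limits by construction.

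**2. Two examples with invented data.**

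- *Checkable by hand.* Reference: 19 subjects at 1 h and 17 at 2 h. Test: the same, except that two subjects move from 1 h to 2 h. The medians are 1 h and 2 h, so their difference is 1 h. The paired differences are 34 zeros and two values of 1 h. Of the Walsh averages, 34 × 35 / 2 = 595 are 0, 34 × 2 = 68 are 0.5 and 3 are 1. The 228th from either end is 0. With zeros kept, the Hodges-Lehmann estimate and both limits are 0 h, against a difference of medians of 1 h. This is an extreme case, but it shows that the two are not linked.
- *Less extreme, simulated, 36 pairs.* Both treatment medians are 2.5 h, so the difference of medians is 0.0 h. The median of the paired differences is 0.5 h and the Hodges-Lehmann estimate is 0.75 h. The 90% CI is 0.25 to 1.25 h with all differences kept, and 0.25 to 1.5 h with the four zero differences dropped. The test with zeros dropped gives p = 0.013.

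**3. How often the estimate falls outside its interval.** All runs use 36 pairs and lognormal tmax. The reference median of 2 h, the spreads, the shifts and the sampling grids are assumptions; the SAP gives none of them.

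| Assumed setting | Difference of medians outside the 90% CI |
|---|---|
| Log-scale SD 0.25 between and 0.35 within subjects; shift 0 / 0.5 h; 9-point grid | 4.4% / 3.8% |
| Same, 7-point grid | 1.0% / 11.6% |
| Same, no grid | 5.2% / 4.8% |
| CV 40% to 60%, test/reference ratio 1.0 to 1.3, correlation 0.3 to 0.6; grid 0.5 to 12 h; zeros kept | 2.6% to 7.2% |
| Same, zeros dropped | 1.3% to 11.1% |
| Same, no grid | 3.5% to 9.2% |

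The first three rows use 4,000 runs per scenario and the last three use 3,000. A further set under similar assumptions gave about 1% to 10%, and there the difference of medians had a larger SD than Hodges-Lehmann in eight of nine scenarios.

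The difference of medians was not equal to the Hodges-Lehmann estimate in about 45% to 64% of gridded datasets (settings of row 4). In the settings of rows 1 to 3 the two were 0.09 to 0.35 h apart on average. On the other reading, the median of the paired differences fell outside in at most 0.3% of datasets in the settings of rows 4 to 6, and in under 1% overall.

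**The case against.** **The reading is not certain.** Section 9.3.2 does not say that the medians are those of each treatment. A median of within-subject differences would suit a paired test, and on that reading falling outside the interval almost never happens. The plural is weak evidence, since the estimates and intervals in the same sentence are plural too. Still, an estimate of the median difference that is based on medians reads more naturally as a difference of two medians. This objection stands in part: the ambiguity belongs in the point.

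**The targets need not differ.** A reader might infer that the estimate and interval always address different parameters. They do not. If the pairs are exchangeable apart from a location shift, the differences are symmetric about that shift, and the difference of medians, the median difference and the pseudo-median coincide. In the simulated zero-shift scenarios all targets are zero, yet 1.0% to 5.2% still fall outside (table rows 1 to 3). There the conflict is sampling noise from an unpaired, less efficient estimator. This objection stands. The targets separate only when the shift model fails.

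**The percentages rest on assumptions.** This stands too. Section 5 gives only sampling windows, up to 48 h for lasmiditan and its metabolites and up to 12 h for propranolol. The largest figure comes from one coarse grid with an assumed 0.5 h shift, and one assumed median of 2 h was used for all analytes.

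**Little depends on it.** The primary objective is heart rate (section 4.1). PK of the two drugs is secondary (4.2) and metabolite PK exploratory (4.3). Section 9.1 already provides medians and listings, so a discrepancy would be visible.

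**Conclusion.** The point holds as an estimator mismatch combined with unclear wording. On the more natural reading, an unpaired estimate stands beside a paired interval that does not constrain it. With 36 pairs it would fall outside its own 90% CI in roughly 1% to 12% of datasets under the assumed distributions and grids, so in most datasets no visible conflict arises. On the other reading the figure is under 1%. That the two estimators are not linked is mathematical and needs no assumption; the percentages are illustrative only.

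A reader might go further and conclude that the tmax test or its interval is invalid, or that a trial conclusion is at risk. The SAP does not support that. The signed-rank test, its interval and its p-value are untouched, the SAP attaches no margin or decision rule to tmax, and only the reported point estimate changes. This is a minor improvement.

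**What to change.** In section 9.3.2, replace the sentence on the tmax estimate with:

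> *The Hodges-Lehmann estimate (median of the Walsh averages) of the pseudo-median of the within-subject tmax differences will be presented with the corresponding 90% CI and p-value from the Wilcoxon signed-rank test, with zero differences handled the same way in all three; observed medians per treatment are descriptive only.*

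The estimate then lies inside its interval by construction, and the two readings disappear. The clause on zeros matters because their treatment moved the upper limit from 1.25 to 1.5 h in the simulated example. Naming the pseudo-median avoids implying that it always equals the median difference, which requires symmetry.

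The cost is one SAP sentence and a small programming change. Design, data collection and the test stay as they are.
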